We will exclude patients with no intraoperative anesthetic records. Cardiac surgery patients (identified by procedure anatomy “Heart” or “Cardiac” within Innovian) are excluded since they have a unique set of considerations and complications due to having surgery directly in the heart. To include the full spectrum of non-cardiac surgical patients, no specific surgeries will be excluded except for deceased organ donation (“organ retrieval” in Innovian procedure name, and American Society of Anesthesiologists classification for neurologically-deceased organ donors, ASA=VI).

Preliminary analysis of our intraoperative database estimates approximately 35,000 patients in this cohort. For patients with multiple procedures, the date of the first surgical procedure with an overnight stay will be used to identify the specific surgical admission of interest.

Data Sources

The de-identified dataset will consist of databases from Innovian, Horizon Surgical Manager (HSM), and Health Data Nova Scotia (HDNS). Innovian is the intraoperative anesthesia electronic information management system used at the QEII, containing automated recordings of intraoperative standard monitors, time-stamped anesthesiology entries of medications and interventions, and perioperative laboratory tests. HSM contains vital signs and administrative data at the anesthetic preoperative clinic, in the preoperative area prior to the surgery, and in the recovery room after surgery.

The specific HDNS databases to which access is being requested are the Canadian Institute for Health Information (CIHI) Discharge Abstract Database (DAD) and Vital Statistics. DAD is a repository of clinical and administrative data from each hospitalization, including preoperative diagnoses, surgery performed, postoperative complications, and investigations.

DAD includes the 25 most relevant diagnoses preoperatively and postoperatively. Nova Scotia physician billings data will not provide any additional relevant information and are not necessary for this project. The Vital Statistics database records all deaths within Nova Scotia. Innovian and HSM data will be linked together by health card number and surgical date by the Innovian Data Manager (Innovian-HSM dataset). The health card numbers will be sent to Medavie for encryption. HDNS will link the Innovian-HSM dataset with the HDNS variables by encrypted study IDs and surgery date. National and provincial privacy and data security policies will be strictly followed.

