 5. Delirium
 6. Septic Shock
2. Postoperative ICU admission (yes/no)
3. Prolonged Postoperative Length of Stay (LOS) (greater than vs. less than or equal to CIHI Expected Length of Stay (ELOS) as assigned by the Case Mix Grouping) [note that the LOS includes the day of surgery]
4. Hospital readmission within 30 days (yes/no)
5. Intraoperative mortality (yes/no)
6. Days alive and out of hospital at 30 days postoperatively (28)

III. Other predictors included into model

The following potential perioperative predictors will be evaluated as covariates during model building. Statistically significant predictors will be retained in the model.

Table 2. Other predictors

Preoperative	
 1. Demographics: age on date of surgery, sex, obesity (body mass index>30) 2. Indicators of preoperative comorbidities: since no comorbidity score has perfect performance, a variety of models will be evaluated and the most significant predictive score will be retained in the model. 
 • American Society of Anesthesiologist class • RCRI score(29), and specific components via ICD codes (history of ischemic heart disease, congestive heart failure, cerebrovascular disease, diabetes, chronic kidney disease, and CCI and Case Mix Group codes of suprainguinal vascular, intraperitoneal, or intrathoracic surgery) using previously published methods (30)(31) • Elixhauser comorbidity index (32) and Charlson Comorbidity Index (33): calculated using diagnoses from the previous three years according to standard algorithm by HDNS. Reported as both total score and individual categories • Hospital Frailty Risk Score (34): based on ICD codes • Preoperative blood pressure: ICD diagnosis of hypertension and by measured blood pressure • Preoperative heart rate: Innovian and HSM • Chronic Obstructive Lung Disease (ICD code): since it may affect the interpretation of results of SpO₂ and EtCO₂ 3. Indicators of surgical complexity 
 • CIHI DAD Case Mix Group (CMG) class (also contains categories that include medical complexity) • Main Surgical Service • Procedural Index for Mortality Risk (PIMR) (35): according to CCI • Procedure: CCI codes • Preoperative ICU admission • Emergency surgery: as determined by DAD Method of Entry = emergency department or transferred from another institution)

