This interdisciplinary study brings together investigators from diverse disciplines and locations, with expertise from Dalhousie anesthesiology, epidemiology, and Big Data Institute, as well as Harvard and University of Toronto. The research project is locally-based and relevant, with findings that may spark further research and inform anesthesiology perioperative practice.

The QEII hospitals are tertiary referral centres taking care of some of the sickest patients of the province. Better understanding of intraoperative predictors may unveil strategies to improve outcome and improve resource allocation after surgery. Moreover, this model may be generalizable to other hospitals, placing the Nova Scotia Health Authority and Dalhousie University as a leading innovator in this area, as large population-level outcomes research will likely continue to be at the forefront of health research.

Research team roles and responsibilities

[name] is completing the Harvard T.H. Chan School of Public Health Summer-Only Master of Science in Epidemiology. This consists of coursework over three summers (2018-2020) and online. The courses focus on epidemiology and advanced statistics, and with mentorship from Harvard and Dalhousie faculty [name] has been learning the theoretical knowledge and practical coding skills to independently analyze this project. She has protected research time to complete this project.

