CIHI DAD	PATIENT_ID: encrypted health card number For HDNS internal use	Patient	Jan 1, 2013 to Dec 1, 2017	HDNS data linkage with Innovian-HSM. The dataset given to us will not contain Patient_ID, but rather a Study ID.
Vital Statistics	PATIENT_ID: encrypted health card number For HDNS internal use	Patient	Jan 1, 2013 to Dec 1, 2017	HDNS data linkage with Vital Statistics. The dataset given to us will not contain Patient_ID, but rather a Study ID.
CIHI DAD	PDATE[1-n]: procedure date	Patient	Jan 1, 2013 to Dec 1, 2017	HDNS data linkage with Innovian surgery date, to ensure that only the admission corresponding to the surgery admission of interest (first surgery admission with LOS>1) is included.

				
The PDATE matching the date of procedure (+/- 1 day) from Innovian will be used. The corresponding number (e.g. PDATE1) will be used for all procedure-related codes (e.g. PCODE1, PDSERV1).
 
Note that except for preoperative comorbidity data, where we would need data for 3 years prior to PDATE, for all other variables we only need data within 30 days after PDATE.

CIHI DAD	
LOS: Length of Stay (after surgery)
 
Derived by HDNS: discharge date minus PDATE + 1 (includes day of surgery)
	Patient	
Jan 1, 2013 to Dec 1, 2018 (to account for prolonged LOS postop from the end of inclusion date)
	
Part of inclusion criteria: if a patient had multiple surgeries, the first surgery with a LOS >1 (i.e. at least overnight stay). To calculate ratio of LOS to Expected Length of Stay (ELOS) as secondary outcome. We have chosen to standardize LOS to only include duration of stay after surgery, since there are many factors that may prolong a patient's stay prior to surgery.

Additional Demographic Information				
CIHI DAD	SEX: Patient sex	Patient	
Jan 1, 2013 to Dec 1, 2017
	
As sex may affect outcomes, this will be included as a covariate in our models
 
M = Male
 
F = Female

HSM	BMI: Body Mass Index [Derived by Innovian]	Patient	
Jan 1, 2010 to Dec 1, 2017
	
Dichotomized according to WHO definition for obesity: BMI>30. This will be combined with ICD code to create a binary Obesity variable (please see below).

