CIHI DAD	
ICU admission [Derived by HDNS]
 
SCUNUM[1-n]: Special Care Unit Num “The SCU Unit Number is a code identifying the type of special care unit where the patient receives critical care.”
 
[Derived by HDNS]
	Patient	
Jan 1, 2013 to Dec 31, 2017
	
Two variables to be derived:
 
 1. Preoperative ICU (yes/no) 2. Postoperative ICU (yes/no) 
Preoperative ICU admission (yes/no) is a covariate to be included into the model. Postoperative ICU admission (yes/no) is a secondary outcome to be included into model. Descriptive statistics will be performed.
 
Derivation process: ICU = yes include the following SCUNUM: 10 = Medical Intensive Care Nursing Unit 20 = Surgical Intensive Care Nursing Unit 25 = Trauma Intensive Care Nursing Unit 30 = Combined Medical/Surgical Intensive Care Nursing Unit 35 = Burn Intensive Care Nursing Unit 40 = Cardiac Intensive Care Nursing Unit Surgery 45 = Coronary Intensive Care Nursing Unit 80 = Respirology Intensive Care Nursing Unit Else ICU = no
 
If the SCU Admit Date is on or before PDATE, then it would be defined as Preoperative AND postoperative ICU admission. Else, postoperative ICU admission only.

CIHI DAD	READMIT: Readmission Code (within 30 days after PDATE) [Derived by HDNS]	Patient	Jan 1, 2013 to Dec 31, 2017	
Readmission within 30 days of PDATE (yes/no) is a secondary outcome to be included into model. Descriptive statistics will be performed.
 
Derived: Postoperative readmission = yes include the following:
 
 1 = Planned readmission from previous acute care 2 = Unplanned readmission within 7 days following discharge from acute care 3 = Unplanned readmission 8 – 28 days following discharge from acute care 4 = ≤ 7 days, unplanned 5 = New patient 9 = None of the above. 
Else Postoperative readmission = no

CIHI DAD	LOS:EOS Ratio of Length of Stay (LOS) to Expected Length of Stay (EOS) as assigned by the Case Mix Grouping [Derived by HDNS]	Patient	Jan 1, 2013 to Dec 31, 2017	
This will be dichotomized by HDNS: LOS:EOS > 1 (yes/no). This is a secondary outcome to be included into model. Descriptive statistics will be performed.

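### No rule covers transfer to another hospital after surgery, so prolonged stay and 30-day readmission may be misclassified for transferred patients

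*Combined protocol and SAP*

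**What the plan says.** **Length of stay.** The LOS row of Appendix 1 defines postoperative LOS as "discharge date minus PDATE + 1 (includes day of surgery". The procedure-date row links the data so that "only the admission corresponding to the surgery admission of interest (first surgery admission with LOS>1) is included".

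**Prolonged stay.** The Outcomes section compares LOS "greater than vs. less than or equal to CIHI Expected Length of Stay (ELOS" as assigned by the Case Mix Grouping. The LOS:EOS row of Appendix 1 (the row expands EOS as expected length of stay) applies the same cut: "This will be dichotomized by HDNS: LOS:EOS > 1 (yes/no".

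**Readmission.** The READMIT row states: "Readmission within 30 days of PDATE (yes/no) is a secondary outcome to be included into model". Codes 1, 2, 3, 4, 5 and 9 all score yes. Code 5 is a new patient and code 9 is none of the above. No transfer category or exclusion is listed.

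**Follow-up window.** The Admit-date and Discharge_date rows take any record with an admission or discharge date from surgery to 30 days after it. They require no gap after the index discharge.

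**Source.** Data Sources says "DAD is a repository of clinical and administrative data from each hospitalization". No section describes joining consecutive records.

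**Transfers.** ADFROM, the sending institution, is used only to classify surgery as emergency. Discharge disposition is used only to identify in-hospital death. The Benefits section describes the setting: "The QEII hospitals are tertiary referral centres taking care of some of the sickest patients of the province".

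**The concern.** A tertiary referral centre may send patients back to another hospital to recover. If such a transfer closes the surgical abstract, one unbroken hospital stay appears as two records. The first gives a short LOS. The second has an admission date soon after surgery and meets the written conditions for a readmission. The same patient can then look better than they were on one secondary outcome and worse on another.

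Days alive and out of hospital at 30 days has no derivation row in Appendix 1, so it is open to the same error if it is built from this LOS.

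These outcomes are to be modelled with the best-performing model. An error that depends on where recovery took place could enter the reported associations.

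**Working it through.** The plan states no transfer, readmission or LOS figure, so there is nothing of its own to reproduce. The check applies the written rules to assumed cases.

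**Inputs from the documents**
- LOS = discharge date − PDATE + 1 (LOS row).
- Prolonged if LOS/ELOS > 1 (LOS:EOS row).
- Readmission = yes for codes 1, 2, 3, 4, 5 or 9 (READMIT row).
- Cohort of about 35,000 (Study Population).

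**Assumed inputs.** ELOS of 5, 7 or 10 days; transfer on postoperative day 3, 5, 8 or 12; final discharge from the receiving hospital on day 14.

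**Step 1: prolonged stay.** With transfer on day *t*, the index record gives LOS = *t* + 1. The whole stay gives 14 + 1 = 15.

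| Transfer day | Index LOS | Ratio, ELOS 5 | Ratio, ELOS 7 | Ratio, ELOS 10 |
|---|---|---|---|---|
| 3 | 4 | 0.80, no | 0.57, no | 0.40, no |
| 5 | 6 | 1.20, yes | 0.86, no | 0.60, no |
| 8 | 9 | 1.80, yes | 1.29, yes | 0.90, no |
| 12 | 13 | 2.60, yes | 1.86, yes | 1.30, yes |
| Whole stay | 15 | 3.00, yes | 2.14, yes | 1.50, yes |

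The entries no and yes give the prolonged-stay label. It differs from the whole-stay label only where *t* + 1 ≤ ELOS, which is 6 of these 12 cases. Where the index part already exceeds ELOS, the truncation does not change the label.

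**Step 2: readmission.** In each case the receiving record's admission date lies within 30 days of surgery, so it is inside the window. Every code listed in the READMIT row scores yes, so the record is a readmission under any of them. Joining the two records changes that to no.

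**Step 3: number exposed.** Assume 2% to 10% of the cohort is transferred out:
- 0.02 × 35,000 = 700
- 0.10 × 35,000 = 3,500

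If 25% to 75% of these changed label on prolonged stay (also assumed):
- Low end: 700 × 0.25 = 175 to 700 × 0.75 = 525
- High end: 3,500 × 0.25 = 875 to 3,500 × 0.75 = 2,625

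**The case against.** **Silence is not a rule.** No section says that a transfer counts as a discharge. That follows from the LOS formula, the single-admission link and the absence of a joining step. HDNS derives these variables and might join consecutive records unprompted. This stands, and it is why the point is worded as what may happen. The plan nevertheless does not ask HDNS to join them.

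**Index LOS over index ELOS is defensible.** ELOS belongs to one abstract. Dividing a multi-hospital LOS by it would tend to label transferred patients as prolonged. This stands too, so episode LOS belongs in a sensitivity analysis and not in the main definition.

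**The READMIT row has a wider fault.** Counting codes 5 and 9 as yes reaches well beyond transfers. Whether a receiving record would still score yes after that is corrected depends on coding rules that the documents do not give. Correcting the codes would not repair LOS.

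**Days out of hospital may escape.** Admission and discharge dates are requested for the 30-day window, so hospital days could be counted across records. That is possible but not stated.

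**Stronger readings a reader might infer.** One is that every transferred patient is scored as not prolonged; the table shows otherwise. Another is that frailty, emergency surgery or instability will look protective for prolonged stay and harmful for readmission. The documents do not say what drives transfer out, and frailty and emergency surgery are candidate covariates, so neither the direction nor the size of any bias is established. A third is that transfers make up a large share of scored readmissions. With transfer share *t* and true readmission rate *r*, *t*/(*t* + *r*) runs from 0.02/0.12 = 17% to 0.10/0.15 = 67%. Neither rate is in the documents, and the formula assumes that every receiving record scores yes and that no transferred patient is truly readmitted.

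**Conclusion.** The gap is real. Applied literally, the derivations can score one continuous stay as not prolonged, as a readmission, or as both. The prolonged-stay error arises only when the index part is at or below ELOS and the whole stay exceeds it. The readmission error arises because the window needs no gap and the READMIT row excludes no transfers.

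Two secondary outcomes are exposed, and days alive and out of hospital is exposed conditionally. Thirty-day mortality comes from Vital Statistics by date of death, so neither the primary outcome nor the mortality comparison with the Surgical Apgar Score is touched.

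The size is unknown. The 700 to 3,500 patients rest on an assumed 2% to 10% transfer share and count those exposed, not those misclassified. The point is worth correcting before HDNS derives the variables, but it does not threaten the main result.

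**What to change.** 1. **READMIT row.** Join to the index episode any DAD record that is an inter-hospital transfer and whose admission date is the same day as, or the day after, the preceding discharge date. Count as readmission only an admission after that episode ends.
2. **Days alive and out of hospital.** Add a derivation row that uses the same episode.
3. **Prolonged stay.** Keep the index-abstract LOS:ELOS as the main definition and flag transferred patients. Add two sensitivity analyses: one with episode LOS, and one excluding transferred patients.
4. **Data request.** ADFROM is requested only to December 1, 2017; extend it to cover receiving records through December 31, 2017. If discharge disposition is used to identify transfers, request it for all patients over that span, because its row now serves only to identify deaths. Discharge_date stops at December 31, 2017, while the LOS row runs to December 1, 2018. Align the two so that episode LOS can be completed for late-2017 surgery.
5. **Reporting.** Give the number transferred out, which replaces the assumed range above.

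The cost is a small change to the data request and a little more programming by HDNS. Episode LOS over a single-abstract ELOS remains inexact, which is why it is confined to a sensitivity analysis.

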The performance of all models created will be evaluated in the validation set as part of internal validation using the same metrics of discrimination, calibration, and risk reclassification, and compared to the Surgical Apgar Score. Since there will likely be significant class imbalance and ROC curves may overestimate model performance, for each model, precision and recall curves (PRC), F score, average precision, and AUC will also be reported and compared. The best performing model will also be used to analyze for predictors for secondary outcomes. Sensitivity (recall, true positive rate), specificity, positive predictive value (precision), G-mean, negative predictive values, False Discovery Rates (FDR), optimism, and measures of association of hemodynamic thresholds for primary and secondary outcomes will be computed. Bayesian network causal inference analysis may be performed, to help increase interpretability.

Sensitivity and subgroup analysis

Sensitivity analysis will be performed for different definitions of hemodynamic derangements. Subgroup analysis will be performed based on age, sex, high preoperative risk (most significant indicator of preoperative comorbidity in Table 2, based on final model), RCRI, frailty (HFRS), preoperative hypertension, a select list of intermediate-high risk, gender-neutral elective surgery (please see Appendix – RCRI Protocol Table 1), emergency surgery, and type of anesthesia.

Power calculation

The 2016-2017 in-hospital mortality after major surgery in Nova Scotia is 1.7% (47). Using the Events Per Variable criterion (EPV) of at least 10 outcomes per predictor in the sample, the 1.7% mortality (408) out of an estimated sample size of 24,000 for the derivation/training group means that our model would be valid for up to 41 predictors for the primary outcome. However, the EPV may over or underestimate the limitations of the EPV criterion (48), square root of the mean squared prediction error (rMPSE) and mean absolute prediction error (MAPE) will be calculated based on the number of predictors, sample size and events fraction (49) with the caveat that this model has not been externally validated. Full power calculation will be performed once we receive the final sample size.

Strengths

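### Secondary outcome 3 uses the LOS:ELOS ratio only as above 1 or not; the plan should also obtain the uncut ratio and prespecify a graded analysis beside the flag

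*Combined protocol and SAP*

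**What the plan says.** The Outcomes section (Variables, II) defines secondary outcome 3 as "Prolonged Postoperative Length of Stay (LOS) (greater than vs. less than or equal to CIHI Expected Length of Stay (ELOS", that is, as a binary variable. The LOS:ELOS row of Appendix 1 (spelled EOS there) has HDNS derive the ratio and then cut it: "This will be dichotomized by HDNS: LOS:EOS > 1 (yes/no".

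The LOS row of Appendix 1 derives post-surgical stay in whole days as "discharge date minus PDATE + 1 (includes day of surgery", and gives one purpose as "To calculate ratio of LOS to Expected Length of Stay (ELOS) as secondary outcome". Its time span runs to Dec 1, 2018, "to account for prolonged LOS postop from the end of inclusion date". The Discharge_date row and the LOS:ELOS row both stop at Dec 31, 2017.

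ELOS has no row of its own. For modelling, Evaluating model performance says: "The best performing model will also be used to analyze for predictors for secondary outcomes". Secondary outcome 6 is "Days alive and out of hospital at 30 days postoperatively".

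**The concern.** Length of hospital stay is one of the outcomes named in the study's objective, and better resource allocation is one of its stated benefits. Resource use depends on how long an overrun lasts, not only on whether one occurred. On the planned outcome a ratio of 1.05 equals a ratio of 5, while 0.98 and 1.02 are opposites. The documents give no reason for analysing only the cut.

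At stake is precision for the less common exposures in Table 1; low oxygen saturation and vasopressor infusion may be among them. For these, the number of exposed patients limits what can be detected. HDNS has to form the ratio in order to cut it, so the graded value exists at the point where it is discarded.

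**Working it through.** **1. The plan's own figure.** The Power calculation section takes 1.7% of 24,000: 24,000 × 0.017 = 408 deaths, and 408 / 10 = 40.8, given as 41 predictors. This reproduces, but it concerns the primary outcome. No effect size, proportion or power target is given for length of stay.

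**2. Information kept by the cut.** Let p be the share with LOS > ELOS (not in the documents; assumed 10% to 50%).
- If log(LOS/ELOS) is normal, the efficiency of the binary analysis relative to an efficient analysis of the log ratio is φ(z)² / [p(1−p)], where z is the (1−p) normal quantile.
- If it is logistic, the efficiency relative to proportional odds is 3p(1−p).
- Loss is 1 minus efficiency. Equivalent N is 24,000 × the normal efficiency.

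| p | Normal efficiency | Loss, normal | Loss, logistic | Equivalent N (normal) |
|---|---|---|---|---|
| 50% | 0.64 | 36.3% | 25.0% | 15,278 |
| 40% | 0.62 | 37.8% | 28.0% | 14,926 |
| 30% | 0.58 | 42.4% | 37.0% | 13,816 |
| 20% | 0.49 | 51.0% | 52.0% | 11,756 |
| 10% | 0.34 | 65.8% | 73.0% | 8,213 |

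LOS is in whole days and stays of 1 day or less are excluded, so ties and a floor of 2 days exist. A simulation that included both still gave a relative efficiency of about 0.64 to 0.66.

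**3. Choice of comparator.** In a lognormal simulation (log-SD 0.9 assumed, shift 0.1 SD, 1,500 replicates), the loss against a linear model on the raw, skewed ratio was about 1% at p = 50%, 10% at p = 30% and 48% at p = 10%. Unless few patients exceed ELOS, the gain comes from the log scale or ranks, not from the raw ratio.

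**4. Power illustration.** Assumed: SD of the log ratio 0.7, p = 40% in the unexposed, two-sided alpha 0.05, unadjusted comparison, N = 24,000.
- Graded: z = ln(1 + effect) / [0.7 × √(1/n1 + 1/n0)].
- Binary: z = (p1 − p0) / √(p1q1/n1 + p0q0/n0), with p1 from the shifted normal.
- Worked case, 2% exposed (480 vs 23,520) and 10% longer stay. Graded: 0.0953 / 0.0323 = 2.95, power 84%. Binary: p1 = 0.453, so 0.0534 / 0.0229 = 2.33, power 64%.

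| Exposed | Longer stay | Graded | Binary |
|---|---|---|---|
| 2% | 10% | 84% | 64% |
| 5% | 5% | 65% | 46% |
| 10% | 5% | 90% | 72% |
| 10% | 10% | >99% | >99% |

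With all 35,000 patients the first two rows become 95% vs 80% and 81% vs 61%.

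**5. Time spans.** For surgery on Dec 1, 2017, discharge data ending Dec 31, 2017 cap LOS at 31 − 1 + 1 = 31 days. A span to Dec 1, 2018 allows 366 days. The flag tolerates the cap once ELOS has been passed; a graded ratio does not.

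**The case against.** Several counter-arguments carry weight.

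- **The percentage.** A reader might take a loss of around 40% as a property of this study. The documents do not support that: it needs an assumed distribution, an assumed proportion above ELOS and an efficient comparator.
- **Withholding.** A reader might infer that HDNS discards the graded data before the team sees any. The documents do not say so. Appendix 1 marks restricted fields, for example "For HDNS internal use" for the encrypted identifier, and the LOS row has no such mark. The Case Mix Group is to be modelled, so LOS adjusted for that group may be possible already. What stands is narrower: nothing requests ELOS or the uncut ratio, so the team is not shown to be able to rebuild it.
- **Another graded outcome.** Days alive and out of hospital grades stay up to day 30, so the outcome set is not blind to the size of an overrun. It stops at day 30 and is not standardised to expected stay, so it is a partial substitute.
- **Coherence of the flag.** The binary form is defined consistently in the Outcomes section and the LOS:ELOS row, and it suits a plan that carries its best classifier over to the secondary outcomes. The ratio wording in the LOS row describes what LOS is for; it is not a rival definition. This argues against replacing the flag, not against adding to it.
- **Limited consequence.** If 10% to 50% exceed ELOS, the derivation set holds 2,400 to 12,000 such patients, against 408 deaths. The power gains are for small effects in unadjusted tests, whereas the plan uses multivariable prediction. That limits the point but does not remove it for uncommon exposures, where the exposed count binds.

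**Conclusion.** The point holds as a precision issue on one secondary outcome. Length of stay relative to expected is analysed only as above 1 or not, and no row asks for what a graded analysis needs. The loss is about 36% to 42% if the log ratio is roughly normal and 30% to 50% exceed ELOS; across 10% to 50% exceeding it is 36% to 66% (normal) or 25% to 73% (logistic). All of these are assumptions. In the illustrative small-effect cases the power difference is 18 to 20 percentage points; for common or large effects it vanishes.

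The stronger conclusion, that the binary outcome is wrong and must be replaced, is not supported. It fits the planned pipeline. A full-scale ratio would also be more exposed to two gaps: the plan states no rule for in-hospital deaths, and the discharge time spans conflict. The primary outcome is unaffected. The change is worth making because it is cheap.

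**What to change.** 1. In the LOS:ELOS row of Appendix 1, ask HDNS to deliver the undichotomised ratio, or LOS and ELOS, together with the yes/no flag. Make the request before linkage is finalised, since the team loses server access after study completion.
2. Keep LOS > ELOS as the defined binary outcome. In the Outcomes section, add a prespecified graded analysis with the same predictors: a linear model on log(LOS/ELOS), or proportional odds on its ranks. Report estimates with confidence intervals. Do not use a linear model on the raw ratio.
3. In Evaluating model performance, state that this analysis uses a continuous or ordinal model, not the mortality classifier.
4. State one rule for in-hospital deaths, applied to both the flag and the graded analysis, so that an early death does not count as a short, favourable stay.
5. Reconcile the time spans of the LOS row (Dec 1, 2018) with the Discharge_date and LOS:ELOS rows (Dec 31, 2017), so that long stays after late-2017 surgery are not truncated.

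The cost is one extra column, one extra non-classifier model, and an effect measure (a ratio of stays or an odds ratio across ranks) that is slightly less familiar than a yes/no rate. If the longer discharge span is not already what HDNS will supply, the request must cover it. No new patients are needed.
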